implementation on sub-anesthetic doses of intravenous ketamine as augmenting strategy of standardized, manually-driven PE in PTSD (*Figure 7*). For this purpose, we aim to: **1) clarify research hypotheses on the efficacy, safety and tolerability of this MEP approach; 2) assess the acceptability of methods and instruments to participants; 3) identify potential barriers to subsequent study completion, and 4) obtain estimates of means, standard deviation and 95% confidence intervals on outcome measures as well as the expected rates of missing data and participant attrition.** We estimate that analysis of data obtained from participation of 10 patients will provide responses to our scientific aims. Participants will be male and female veterans (18 to 75 years old) of any era or military background diagnosed with PTSD. Potential participants will be recruited from Mental Health clinics and screened for eligibility using a two-stage process (phone/chart review, followed by interview). Those who meet eligibility criteria will complete baseline assessment one week prior to starting treatment. Then, treatment will consist of 1) 3-week ketamine-PE phase composed by weekly single intravenous ketamine (0.5 mg/kg for 40 minutes) followed within 24 hrs. by PE session; and 2) ketamine-free PE phase from week 4 through 12. After PE is completed (session 12), patients will be assessed during a 2-month follow-up period at various time points. We estimate that 10 veterans will reach time point for primary outcome measure (CAPS score at week 12) and will be considered for primary analysis. Independent evaluation of PTSD, cognitive function, depression, anxiety and other potential covariates (i.e., pain) will be ascertained at baseline, at several time points during treatment, and at follow-up.

D.1.1. Design Considerations: As with any pilot study, several factors have been considered in the design of this proposal. The goal is to provide a design that is feasible, efficient, and above all, able to answer study aims. Some of the possible alternative designs, and reasons we did not select them, are listed.

Table 2. Considerations and Rationale for Choosing the Current Design

Consideration	Rationale

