Single vs repeated ketamine infusions.	Our pilot study(Albott et al., 2018) demonstrated that repeated ketamine infusion provides higher efficacy (80% remission) as compared to single infusion (24.1% CAPS-IV score<50)(Feder et al., 2014). Mild transient increases in dissociative symptoms without the emergence of mania or psychotic symptoms were similar in both studies.

Number of ketamine infusions	During PE, session 1 and provide a rationale of PE and understanding of trauma. Imaginal exposure (IE) begins at session 3. Two independent studies(Foa et al., 2002) (Larsen et al., 2016) found post-IE exacerbation of PTSD, anxiety, and depressive symptoms at session 4. We will measure the effect of administering three single ketamine treatments prior to IE aiming to target a key component of PE with the potential to enhance the efficacy PE outcomes.
Inclusion of comorbid condition to PTSD.	Traumatic experiences have a variety of psychiatric sequelae, often including multiple comorbid psychiatric diagnoses. Depressive disorders have been found to co-occur in most individuals who develop PTSD(Rytwinski et al., 2013) and may act as an indicator of a more severe response to trauma exposure. The high rates of comorbidity between PTSD and depression have thus led to suggest that their co-occurrence may be better conceptualized as a general traumatic stress construct, rather than discrete co-occurring disorders (Dekel, Solomon, Horesh, & Ein-Dor, 2014) (Bedard-Gilligan et al., 2015)
Wash-out vs a period of stable doses of current psychotropic medications.	Patient taking psychotropics with potentially serious drug-drug interactions with ketamine (e.g., barbiturates) will be excluded. The therapeutic effect of psychiatric medications is prolonged beyond clearance of active compound or their metabolites from blood and brain so pharmacological "isolation" of ketamine will not likely occur with a brief medication washout. Washout from psychiatric medications would 1) limit recruitment and result in a sample that is not characteristic of many veterans seeking treatment; 2) raise ethical concerns as severe conditions (e.g., agitation) require rapid stabilization usually through pharmacological interventions. However, keeping stable doses for at least 4 weeks of prior psychotropic regimen will decrease confounding effects on the study of ketamine on PTSD, depression, and anxiety.

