Our planned enrollment includes 10 patients to receive three weekly ketamine-PE treatment followed by ketamine-free PE treatment for 9 additional weeks. Participants will be recruited from veterans receiving mental health treatment. Referrals will occur from VA clinicians and clinics, and responses from posted fliers and study pamphlets. Potential participants will be provided with information about the study and screened through medical records, chart review, and by telephone to determine whether they meet basic inclusion/exclusion criteria. Those who qualify will be scheduled for a more rigorous assessment (*see further details below*).

D.3.1. Eligibility Criteria: The following eligibility criteria will be used to identify a broad array of participants with PTSD considered suitable for the study.

Table 3: Eligibility Criteria

Inclusion Criteria	Exclusion Criteria

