*Patient will be monitored an hour after infusion or hourly until vital signs, side effects from ketamine return to pre-infusion measures and mAldrete score ≥ 9 .

D.4.2. PE therapy: PE is an evidence-based psychotherapy for PTSD that is based on the Emotional Processing Theory of PTSD; the four components of PE are: 1) exposure to safe situations, objects, or people that cause distress and are avoided because they are trauma reminders (in vivo exposure), 2) revisiting and processing of the trauma memory (imaginal exposure), 3) psychoeducation about trauma-related symptoms, and 4) breathing retraining(Rothbaum, 2007). Session 1 includes the presentation of treatment rationale and program overview, information gathering, and breathing retraining. Session 2 includes education about common reactions to trauma, rationale for in vivo exposure, and construction of an in vivo exposure hierarchy. The hierarchy includes safe or low-risk activities and situations that were avoided because of their association with the trauma. Throughout the treatment, participants will be assigned homework to confront items on the hierarchy in a gradual fashion, working up to the most anxiety-arousing situations. During Session 3, the rationale for confronting the trauma memory in imagination is presented and initiation of imaginal exposure and processing is conducted. In this procedure, participants will be asked to close their eyes, visualize the trauma, and recount it aloud in the present tense for 45–60 min. The memory recounting will be repeated if necessary to allow total reliving of 45–60 min. The exposure will be audiotaped; participants will be instructed to listen daily to the tape. Sessions 4–10 will be conducted in a similar fashion: therapists review homework, conduct imaginal exposure to trauma memory for 30–45 min, discuss the imaginal exposure, and assigned in vivo and imaginal exposure homework. In the final session, participants summarize learning in treatment, discuss their progress, plans, and relapse prevention

D.5. Assessment Procedures.

Assessments will take place in two contexts:1) at baseline, throughout treatment, and at follow-up, and 2) during each infusion. These assessments are summarized in Table 5. Clinical interviews will be conducted by trained evaluators. Subject compensation will also be provided to increase participant retention and reduce missed assessments (see further details below).

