assessment at the beginning of the protocol; and 3) receive reliability checks on their evaluations throughout the protocol. Initial competency will be established by on-site didactic training for all clinical assessments and data collection procedures followed by the establishment of inter-rater reliability. Inter-rater reliability will be accomplished using a train-to-criterion protocol with recorded patient interviews (for symptom scales all total scores will be required to be within 2 points of the standardized score and all individual item scores were required to be within 1 point of the standardized score; for diagnostic assessments 100% agreement will be required for the primary diagnosis). To maintain competency and reduce “drift,” in-person didactic re-training sessions will be conducted annually and inter-rater reliability established at 6-month intervals to ensure that they meet at least 80% reliability of their measurement. Remediation and additional training will be provided as needed until competency was achieved.

D.5.6. PE Training, fidelity and supervision: Licensed doctoral-level psychologists and masters-level clinical social workers will deliver the PE treatment. Therapists will be existing VA clinicians who have been approved to donate time to the study and treat participants as part of their regular caseload. Supervision of PE will include regular review of session video to determine presence or absence of essential PE component, and monitor for protocol violations. Treatment sessions will be videotaped and 12% will be randomly selected and reviewed by PE expert ([name]) to ensure fidelity to the treatment manual (15 sessions will be selected from sessions 1–2, session 4, sessions 6–9, and sessions 10 and above).

D.6. Outcome Measures.

D.6.1. Primary Outcome Measure: The primary outcome is the difference in PTSD symptom severity from baseline to week 12 measured by the 30-item **CAPS-5** past month version (for current PTSD) total score(Weathers et al., 2018).

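### The expert's random PE fidelity sample cannot include session 3, which on a weekly schedule is the only imaginal exposure delivered within 24 hours of ketamine

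*Combined protocol and SAP*

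**What the plan says.** Section D.5.6 describes two uses of session video. The first is supervision: "Supervision of PE will include regular review of session video to determine presence or absence of essential PE component, and monitor for protocol violations". No number of tapes, choice of sessions or form of reporting is given for it. The second is a sampled review: "Treatment sessions will be videotaped and 12% will be randomly selected and reviewed by PE expert", specified in parentheses as "15 sessions will be selected from sessions 1–2, session 4, sessions 6–9, and sessions 10 and above".

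Section D.1 sets out a "3-week ketamine-PE phase composed by weekly single intravenous ketamine (0.5 mg/kg for 40 minutes) followed within 24 hrs. by PE session", then PE without ketamine from week 4 to week 12. Section D.4.2 places the first imaginal exposure in the last ketamine week: "During Session 3, the rationale for confronting the trauma memory in imagination is presented and initiation of imaginal exposure and processing is conducted". That exposure lasts 45–60 minutes. Sessions 4–10 repeat imaginal exposure for 30–45 minutes.

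Table 2 (row on the number of infusions) justifies giving three infusions ahead of imaginal exposure as "aiming to target a key component of PE with the potential to enhance the efficacy PE outcomes". Its row on open-label design says the pilot is there to test whether ketamine and PE can feasibly be used together. Section D.6.3 takes session 3 as the first imaginal exposure for the peak and mean SUDS scores, to be set against the last one (sessions 10–12).

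**The concern.** The list in D.5.6 names every session number from 1 to 12 except 3 and 5, and gives no reason for the omission. Session 5 matters little, because sessions 4 and 6–9 are of the same kind and are covered. Session 3 has no such substitute. It introduces the rationale for imaginal exposure, its exposure is longer than in later sessions, and it is where an infusion and imaginal exposure meet.

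At stake is what the pilot can say about delivery. If therapists depart from the manual in session 3, for instance because a patient is still affected by the previous day's infusion, the expert's sample has no way of showing it. The report could then describe adherence in the sessions around the combination, but the expert review would say nothing about the combination itself. The first SUDS anchor also comes from a session that the expert never sees.

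**Working it through.** **Inputs**
- Patients: 10 (D.3: "Our planned enrollment includes 10 patients to receive three weekly ketamine-PE treatment followed by ketamine-free PE treatment for 9 additional weeks").
- PE sessions per patient: 12, being 3 with ketamine and 9 without (D.1: "After PE is completed (session 12), patients will be assessed during a 2-month follow-up period").
- Sampling fraction 12%; sample size 15; eligible sessions 1, 2, 4, 6, 7, 8, 9, 10, 11 and 12 (D.5.6).
- One PE session per week. This is an inference, but a well-supported one: D.5.2 puts the ketamine-free assessments at weeks 4, 6, 8 and 12, and Section E pays for them at post-ketamine PE sessions with the same four numbers.

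**1. Reproducing the plan's 15**
- All sessions: 10 × 12 = 120 tapes; 0.12 × 120 = 14.4, rounded up to 15. The stated figure reproduces.
- Listed sessions only: 10 × 10 = 100 tapes; 0.12 × 100 = 12. Fifteen tapes would be 15/100 = 15% of these.

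So the count fits a frame of all 12 sessions, while the list describes a frame of 10.

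**2. What the list leaves out**
- Sessions 3 and 5: 2 × 10 = 20 tapes; 20/120 = 17% with no chance of selection.
- Session 3 alone: 10 tapes, which are all the planned imaginal exposures within 24 hours of ketamine.

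**3. What the expert would see**

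The plan does not say how the 15 tapes are divided. In proportion to the listed sessions:
- Sessions 1–2: 15 × 20/100 = 3 tapes, ketamine-paired, before imaginal exposure starts.
- Session 4 onward: 15 × 80/100 = 12 tapes, from the ketamine-free phase.
- Ketamine-paired imaginal exposure: 0 tapes, however the 15 are divided.

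**4. What widening the frame would give**

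With N tapes in the frame, 10 of them from session 3, and 15 drawn at random: expected session-3 tapes = 15 × 10/N, and P(none) = C(N−10, 15)/C(N, 15).

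| Frame | N | Expected session-3 tapes | P(at least one) | P(none) |
|---|---|---|---|---|
| As listed | 100 | 0 | 0% | 100% |
| Session 3 added | 110 | 1.36 | 78% | 22% |
| All 12 sessions | 120 | 1.25 | 75% | 25% |

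Adding session 3 to the list makes it eligible but does not guarantee that it is seen. Only a reserved number of tapes does that.

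**5. What a small reserve can and cannot show**

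If every reserved tape were adherent, the exact 95% lower limit for the adherence proportion is 0.025^(1/n): 29% for n = 3 and 40% for n = 4. Such a reserve supports description, not estimation of a rate.

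**The case against.** A reader might infer that delivery of the trial's key component goes unchecked. The documents do not support that. The component named in Table 2 is imaginal exposure, not session 3, and the expert can draw imaginal exposure tapes from session 4, sessions 6–9 and session 10 on. Supervisory video review excludes no session. Section D.6.3 has SUDS recorded every 5 minutes during imaginal exposure, so a 45–60 minute exposure should leave about 9 to 12 entries (45/5 to 60/5). A shortened exposure would leave fewer and an omitted one none, for every patient. The exposure is also audiotaped (D.4.2), and the assessments set between infusion and PE session (D.5.2) would help to show a delay.

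Nor should the expert review be read as an independent audit that yields a fidelity rate. D.5.6 does not call the PE expert independent, and it defines neither a rate nor a threshold.

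Two further arguments have some force. Section A.3 puts the clinical durability of ketamine at 7–14 days after one infusion and 16–26 days after repeated infusions, so on the plan's own account a session 4 one week later still falls within ketamine's effect. And because 15 matches 12% of all 120 sessions, the list may simply be incomplete rather than a deliberate exclusion.

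What stands is that the gap is narrow: it concerns the quality of manual adherence in session 3, not whether exposure took place. It does not disappear. SUDS counts show duration, not adherence; supervision of unstated extent guarantees no session-3 review; session 4 has different content and is not the session within 24 hours of infusion; and an incomplete list, followed as written, has the same effect as a deliberate exclusion.

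**Conclusion.** The point holds in a limited form. As written, the expert's random review cannot select session 3 or session 5: 20 of 120 planned tapes, including all 10 imaginal exposures within 24 hours of ketamine. The sample covers ketamine-paired sessions without imaginal exposure, and imaginal exposure in the ketamine-free phase, but not the two together. Only supervisory video review of unstated extent could reach session 3.

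This rests on one PE session per week and, for the counts, on all 10 patients completing 12 sessions. Dropout would reduce the tapes but leave the exclusion unchanged. At the earlier ketamine pilot's 2 in 16 (section 6.8), with every dropout missing all sessions, 120 × 14/16 = 105 tapes would remain.

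The week-12 CAPS-5 outcome and the planned descriptive analyses do not depend on the fidelity sample. What is affected is the evidence that ketamine-paired imaginal exposure followed the manual, which bears on the stated purpose of the pilot. That makes it worth correcting, since the correction is cheap.

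**What to change.** Revise the sampling sentence in D.5.6:
- Keep 15 tapes and the same reviewer.
- Add session 3 as its own stratum with a small fixed number of tapes, for example 3 or 4, each from a different patient.
- Put session 5 with session 4 or with sessions 6–9.
- Describe the session-3 adherence findings separately, in words and counts, without presenting 3 or 4 tapes as a precise rate.

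If session 3 was left out on purpose, state the reason and say how many session-3 tapes supervision will review and how the findings will be recorded.

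The cost is one sentence and 3 or 4 fewer tapes from the other sessions, leaving 11 or 12 of the 15. No extra staff or recordings are needed, and nothing changes in treatment.

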Given that ketamine preferentially activates mPFC, we also hypothesize that ketamine will exert its therapeutic effect on the expression/consolidation of extinction memory (Santini, Ge, Ren, Pena de Ortiz, & Quirk, 2004) without interference of within-session extinction. As extinction memories are labile and fragile, ketamine could bolster the formation, persistence, and possibly context independence of extinction

memories and thus, preventing relapse. This proposed mechanism received support from a recent study using a rodent paradigm for preclinical assessments of PTSD. Girgenti⁷ and colleagues demonstrated that a single dose of ketamine followed by extinction training for three consecutive days enhances the recall of extinction learning (i.e., reduced freezing behavior to cue) and decreases fear renewal 8 days later. This study also showed that ketamine plus extinction exposure increased synaptic proteins promoter (mTORC1) and neuronal activation (cFos) in the mPFC. Moreover, AMPA receptor inhibitor (NBQX) partially but significantly blockaded the effects of ketamine supporting previous findings that the rapid ketamine effect

requires activation of AMPA receptors (Zarate & Machado-Vieira, 2017) and that AMPA receptor agonist infused systematically or directly into the mPFC facilitate contextual fear extinction (Milad & Quirk, 2002) (Zushida, Sakurai, Wada, & Sekiguchi, 2007) (Zarate & Machado-Vieira, 2017). While this study did not specifically elucidate the role of IL-mPFC in the enhancement of fear extinction by ketamine, optogenetic stimulation of the IL-mPFC produces behavioral and synaptic responses similar to the antidepressant actions of systemic ketamine (Fuchikami et al., 2015). Other mouse studies (Ju et al., 2017) of PTSD have revealed that the long-term treatment with ketamine in combination with extinction training may accelerate extinction of fear memories by normalization of DNA methylation of BDNF gene leading to an increased in the levels of BDNF in the mPFC and hippocampus.

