D.5.1. Eligibility and Baseline Assessment: The Eligibility and Baseline Assessment (EBA) will be accomplished during 1-2 visits over a 7 -day period prior to starting treatment. It will take a total of 3 hours. Provisional diagnosis of PTSD and its severity would be obtained by PCL-5 score >33 . The CAPS-5 would be then administered to establish PTSD diagnosis. The M.I.N.I. International Neuropsychiatric Interview (M.I.N.I. 6.0)(Sheehan et al., 1998) will be used for psychiatric evaluation to confirm the absence of exclusionary diagnoses. Lack of moderate/severe cognitive impairment will be ascertained with an MMSE score ≥ 28 . Evaluation of exclusionary criteria involving unstable medical illnesses will be based on brief physical examination, medical record review by study M.D. in consultation with on-site study

anesthesiologist, basic metabolic laboratory tests, and ECG. A urine pregnancy, if applicable, and drug screen will also be obtained. Secondary outcomes at baseline will include cognitive function (CogState), severity of depressive symptoms (MADRS), levels of anxiety (Beck Anxiety Inventory-BAI), suicide risk (Columbia- Suicide Severity Rating Scale- C-SSRS), pain intensity (Numeric Rating Scale-NSR for pain), clinical impression of illness severity (Clinical Global Impression-CGI) quality of life (World Health Organization Quality of Life-Brief-WHOQOL-BREF), and expectation of treatment (CEQ).

D.5.2. Treatment Assessment: The research staff will measure PTSD symptoms severity by administering the CAPS-5 at weeks 4, 12 and 2-month follow-up. Secondary outcomes that includes cognitive function, anxiety, depression, pain, suicide, and general side effects (Patient Rated Inventory of Side Effects- PRISE/ Frequency, Intensity, and Burden of Side Effects Rating-FIBSER) will be obtained 24 hrs. post-ketamine and prior to PE session at week 1, 2, and 3 (ketamine-PE phase). We will administer rating scales again at week 4, 6, 8, and 12 (ketamine-free phase), and at 2-month follow-up. Fear activation and extinction during PE sessions would be measured by the Subjective Units of Distress Scale (SUDS).

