D.5.3. Follow-up Assessment: Following completion of treatment, participants will attend Post-Treatment Assessment monthly for 2 months (total of 02 follow-up visits). Each visit will take about 2 hours. Follow-up assessments will involve self-report for PTSD symptoms (PCL-5), cognitive assessment (CogState), depressive symptom severity (MADRS), clinical impression of illness severity and improvement (CGI), as well as self-reported measures of pain intensity (NRS for pain), level of anxiety (BAI), suicide risk (C-SSRS), general adverse events (PRISE/FIBSER) and quality of life (WHOQOL-BREF). The CAPS-5 will be administered once at 2-month follow-up.

Table 5: General Assessment Schedule

Construct	Measure	Eligibility and Baseline Assessment	Treatment Assessments	Follow-Up Assessment
		1-2 weeks	Week 1 to 12	2 months
Primary Outcome Measure				
PTSD symptoms	CAPS-5	X	X	X
Interview Based Assessments				
Decision-making capacity	Dysken Screening Tool	X		
PTSD severity	PCL-5	X	X	X
Diagnostic interview for comorbid conditions	M.I.N.I.	X		
Rule-out moderate/severe cognitive impairment	MMSE	X		
Infusion Safety Measures				
Physical Exam/ECG/Pregnancy test/Urine toxicology		X		
Recovery from infusion	mAldrete		X	
Side Effects (dissociative, psychotogenic, and manic symptoms)	CADSS, BPRS+, YMRS		X	
Secondary Outcome Measures				
Subjective units of distress (a proxy for extinction)	SUDS		X	
Cognitive function	CogState	X	X	X
Depressive Symptoms	MADRS	X	X	X
Suicide Risk	C-SSRS	X	X	X
Anxiety Symptoms	BAI	X	X	X
Pain Intensity	NRS	X	X	X
Quality of Life	WHOQOL-BREF	X	X	X
General Adverse Events	PRISE/FIBSER		X	X
Global Rating of Illness Severity and Improvement	CGI	X	X	X
Credibility/Expectation of Outcome Treatment	CEQ	X		

D.5.4. Independent Evaluation Integrity: The PI will oversee assessment core to ensure that independent evaluators will 1) undergo standardized training in all assessment instruments, 2) demonstrate reliability of

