D.6.3. Secondary Outcome Measures: Severity of depression would be measure by the **MADRS**, a semi-structured 10-item scale designed to be particularly sensitive to change over time in patients treated with antidepressant medication. The MADRS is psychometrically sensitive to assess the rapid onset of antidepressant efficacy (Johnson et al., 2016). The **PCL-5** is a 20-item self-report measure that assesses the 20 DSM-5 symptoms of PTSD. For the study, the PCL-5 will serve to screen potential candidates for PTSD and to monitor symptom changes during and after treatment. A PCL-5 cut-point score of 33 has been advised as a reasonable value until further psychometric work is available. The time frame for PCL-5 has been modified to meet research needs as in other studies (e.g., NCT02655692). Moreover, the Mental Illness Research, Education and Clinical Centers (mirecc.va.gov) stated that “The PCL can be easily modified to fit specific time frames or events. For example, instead of asking about ‘the past month,’ questions may ask about ‘the past week’ or be modified to focus on events...”. The **BAI** will serve as the gold standard self-report measure of general anxiety symptoms to distinguish anxiety from comorbid conditions such as depressive symptoms. The **C- SSRS- last visit version** will be used to count prospective or treatment emergent suicidal behaviors. The C- SSRS has been used in many treatment trials, and to measure treatment emergent suicidal events during pharmacotherapy(Mann et al., 2006). **SUDS**(Jaycox, Foa, & Morral, 1998) is a self-rating measure of distress ranging from 0 (complete relaxation) to 100 (maximum distress) and will measure activation of fear structure, decrease in fear during exposure sessions (within-session extinction); and decrease in initial reactions to the feared stimuli across sessions (between- session extinction). SUDS ratings correspond well with other indices of fear expression, including physiological indicators. Based on the PE protocol, the therapist will initially generate with the patient anchor examples at 0, 25, 50, 75, and 100 (e.g., 25: riding a roller coaster). SUDS will then be recorded every 5 min during the imaginal exposure. Peak SUDS scores, highest reported distress during first (Session 3) and last imaginal exposure session (Session 10-12), and mean SUDS scores, average reported distress during first (Session 3) and last imaginal exposure (Session 10-12), will be calculated. **NRS** (Ferreira-Valente, Pais-Ribeiro, & Jensen, 2011) is a one-dimensional measure of pain intensity in adults. The NRS is a segmented numeric version of the visual analog scale in which a whole number (0–10 integers) is selected to reflect the intensity of their pain anchored at 0 representing “no pain” and at 10 representing “worst pain imaginable”. The **CGI** (Busner & Targum, 2007)is a brief assessment consisting of a 3-item observer-rated scale that measures illness severity, global

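### SUDS is meant to measure within-session extinction, but the peak and mean scores planned cannot show whether distress falls or rises during a session

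*Combined protocol and SAP*

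**What the plan says.** D.6.3 gives SUDS three tasks. It is to measure fear activation, "decrease in fear during exposure sessions (within-session extinction", and also "decrease in initial reactions to the feared stimuli across sessions (between- session extinction". D.5.2 repeats the purpose: "Fear activation and extinction during PE sessions would be measured by the Subjective Units of Distress Scale (SUDS". Table 5 lists it among the secondary outcomes as "Subjective units of distress (a proxy for extinction".

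A.6.1 explains why the within-session part matters. Ketamine is expected to act on the consolidation and expression of extinction memory "without interference of within-session extinction".

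On data, D.6.3 states: "SUDS will then be recorded every 5 min during the imaginal exposure". On scores, it defines "Peak SUDS scores, highest reported distress during first (Session 3) and last imaginal exposure session (Session 10-12", and the mean at the same two sessions. No start-to-end, peak-to-end or slope score appears there or elsewhere. Section 6.7.3 says change in the secondary measures will be examined descriptively; it does not name SUDS. Section 6.8 lists imputation, last observation carried forward and completers-only analysis for missing values, without saying how they apply to SUDS.

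**The concern.** Within-session extinction is a fall in distress from early to late in one exposure, so a score for it must use the time order of the ratings. Peak and mean do not. Comparing them between session 3 and the last exposure addresses fear activation and change across sessions. It leaves the third stated construct without a summary.

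At stake is one half of the mechanism the plan sets out: consolidation enhanced, within-session learning left alone. D.1 gives clarifying hypotheses, and estimating means, SDs and confidence intervals, as pilot aims. Followed literally, the plan produces no such estimate for within-session change to carry into the later trial. If a score is chosen only after the ratings have been seen, the choice is open to selection.

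**Working it through.** The plan gives no figure to reproduce here. The check is whether the planned scores can distinguish falling from rising distress. All SUDS series below are illustrative assumptions.

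**1. Order of ratings.** For ratings x1, ..., xn, peak = max(xi) and mean = (sum of xi)/n. Both are unchanged when the series is reversed, whereas x1 − xn changes sign.

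| Series | Peak | Mean | First − final | Peak − final |
|---|---|---|---|---|
| 90, 80, 70, 60, 50 | 90 | 350/5 = 70 | +40 | 40 |
| 50, 60, 70, 80, 90 | 90 | 350/5 = 70 | −40 | 0 |
| 80, 75, 70, 65, 60, 50, 45, 40, 35, 30 | 80 | 550/10 = 55 | +50 | 50 |
| the same ten, reversed | 80 | 55 | −50 | 0 |
| 55, 55, 55, 55, 80, 55, 45, 45, 50, 55 | 80 | 55 | 0 | 25 |

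The last three rows share peak and mean, and differ completely in within-session change. Peak minus final cannot be negative, so the direction of change comes from first minus final.

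**2. What peak and mean do tell.** With peak P, mean M and n ratings, the ratings fall short of P by n(P − M) in total. The size of first minus final is therefore at most the smaller of P and n(P − M). For n = 10 and P = 80:

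- M = 55: 10 × 25 = 250, so the cap is 80 and the range is −80 to +80.
- M = 75: 10 × 5 = 50, range −50 to +50.
- M = 79: 10 × 1 = 10, range −10 to +10.
- M = 80: no change is possible.

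The range is always symmetric about zero. The two scores limit the size of a change and never give its direction.

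**3. Unequal exposure length.** D.4.2 gives 45–60 minutes of imaginal exposure in session 3 and 30–45 minutes in sessions 4–10. At 5-minute spacing, counting a rating at the start, that is 10–13 and 7–10 ratings. Assume distress starts at 80 and falls 4 points per rating:

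- 7 ratings: mean 80 − 4 × 3 = 68; first − final 4 × 6 = 24.
- 13 ratings: mean 80 − 4 × 6 = 56; first − final 4 × 12 = 48.

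The same rate of fall gives different means and different change scores, so a whole-exposure score alone would mix rate with duration. A 30-minute window fits within both stated ranges.

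**4. Patients whose exposure ends before session 10.** A.2 cites 38% dropout from PE in one multi-centre trial: 0.38 × 10 = 3.8. Section 6.8 cites 2 of 16 in the team's own ketamine series: 2/16 = 12.5%, and 0.125 × 10 = 1.25. If all leave between sessions 3 and 10, about 1 to 4 of 10 are affected. Neither source matches this trial: the first had no ketamine and the second was an infusion series without PE. Neither figure comes with the timing of dropout.

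**The case against.** The strongest reply is that nothing is lost. The ratings are recorded, D.6.3 does not say other scores are barred, and 6.7.3 promises descriptive change in secondary measures. The non-interference statement sits in the background rationale and is not named among the four aims in D.1. Table 2 says the purpose is feasibility rather than formal evidence of efficacy. All of this stands and limits the importance of the point. It does not supply the missing score.

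A reader might go further in four ways that the documents do not support.

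- *That peak and mean say nothing about within-session change.* They cap its size, as shown in the working; only the direction is missing.
- *That a within-session score would test the hypothesis.* The study is single-arm and open-label. With one session a week, session 3 is both the only imaginal exposure that follows an infusion within 24 hours and the patient's first imaginal exposure. Any contrast with later sessions confounds ketamine with practice, and with exposure length unless a common window is used.
- *That the first-to-last comparison is confined to patients who reach session 10.* Section 6.8 provides for last observation carried forward. What is unclear is which observation is carried. If it is the last exposure attended, the rule works. If only the defined scores count, session 3 is carried forward and zero change is imposed.
- *That 4 of 10 patients will lack a last-session value.* That is only the upper end of an assumed range.

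**Conclusion.** The point holds in a limited form. D.6.3 names within-session extinction as something SUDS measures, and the peak and mean it defines cannot show whether distress fell or rose within a session. This follows from the definitions and needs no assumption about the data. Two sessions with identical planned scores can differ by 80 points in first-minus-final change (+40 against −40 in the five-rating example).

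The consequence is modest: an undefined derived score for one secondary outcome in a descriptive study of 10. No primary result, safety review or data collection depends on it. The last-session matter is smaller still, and its size of about 1 to 4 of 10 rests on borrowed dropout rates and on all dropout falling between sessions 3 and 10.

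**What to change.** In D.6.3, with a matching line in 6.7.3:

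1. Define first-minus-final and peak-minus-final SUDS for each imaginal exposure from the 5-minute ratings. Compute both over a common window, for example the first 30 minutes, and over the whole exposure, with exposure time shown.
2. Report mean, SD and 95% CI for session 3 and for later sessions.
3. State that, with no control arm and with session 3 being the first imaginal exposure, these scores describe within-session change and cannot establish non-interference by ketamine.
4. Where imaginal exposure ends before session 10, state that the carried-forward analysis under 6.8 uses the last imaginal exposure attended, with its session number, beside the completers-only result. This does not help a patient who leaves before session 3, who has no first-exposure value either.

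The cost is a few sentences and slightly more descriptive output. No new data, visits or staff are needed.
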